#### 4.2.2 Secondary and Exploratory Outcome Variables/Endpoints (if applicable)

**Secondary outcomes:** These include physical health, psychiatric symptoms, substance use and recidivism, with mediators including mastery self-efficacy, empowerment and hope.

Recidivism:

Recidivism will be assessed through the public access criminal database called ctlookup.org

Physical health:

Physical health will be measured by the SF-12. The SF-12 has good internal consistency (Cronbach alpha coefficients of 0.72 to 0.89); test retest reliability ( $r = 0.73-0.86$ ).

Psychiatric symptoms:

The 9-item PHQ-9 will measure depression. Reliability and validity of the tool have indicated it has sound psychometric properties. The Beck Anxiety Inventory will be used to assess Anxiety.

Wellness:

Overall Wellness will be measured by the 8 Dimensions of Wellness Measure which assesses physical, environmental, spiritual, social, emotional, financial, occupational, and intellectual wellness (Swarbrick 2012). Wellness goals for each of the 8 dimensions, activities engaged in, and an self-assessment of where participants are currently and where they would like to be with respect to each of the 8 dimensions will be also logged in the coaching measure at peer coaching sessions.

# 5 Study Participants

## 5.1 Study Population

- At least thirty (**N=30**) financial coaches and criminal justice service providers from the New Haven area will participate in training activities during the project's first year as part of our partnership with the NH-FEC and local organizations providing services to the target group. The training will be repeated twice more, in years 2 and 3, to provide refresher training to people already trained, and to train any interested newly hired service providers. At the end of years 1, 2, and 3, people who received that training will be recruited to participate in an online focus group to discuss the intervention (3 focus groups over 3 years with 10 participants each) (**N=30**).
- At least ten (**N=10**) staff working for banks or credit unions in the New Haven area will also participate in training activities during the project's first year as part of our partnership with local banks and credit unions through the BankOn Connecticut Coalition (run by our partner organization, CAHS). The training will be repeated twice more, in years 2 and 3, to provide refresher training to people already trained, and to train any interested newly hired staff. At the start of years 2, 3, and 4, people who participated in the training for bank and credit union staff will be recruited for a focus group (3 focus groups over 3 years with 10 participants each) (**N=30**).
- This research study will enroll 204 people (**N=204**) who have been released from jail or prison 24 months ago or less and who have mental health challenges.

## 5.2 Number of Participants

At least thirty (**N=30**) financial coaches and criminal justice service providers from the New Haven area will participate in training activities during the project's first year as part of our partnership with the NH-FEC and local organizations providing services to the target group. The training will be repeated twice more, in years 2 and 3, to provide refresher training to people already trained, and to train any interested newly hired service providers. At the end of years 1, 2, and 3, people who received that training will be recruited to participate in an online focus group to discuss the intervention (3 focus groups over 3 years with 10 participants each) (**N=30**).

- At least ten (**N=10**) staff working for banks or credit unions in the New Haven area will also participate in training activities during the project's first year as part of our partnership with local banks and credit unions through the BankOn Connecticut Coalition (run by our partner organization, CAHS). The training will be repeated twice more, in years 2 and 3, to provide refresher training to people already trained, and to train any interested newly hired staff.
- At the start of years 2, 3, and 4, people who participated in the training for bank and credit union staff will be recruited for a focus group (3 focus groups over 3 years with 10 participants each) (**N=30**). This research study will enroll 204 people (**N=204**) who have been released from jail or prison 24 months ago or less and who have mental health challenges

### 5.3 Eligibility Criteria

- Participants must be 1) at least 18 years of age; 2) have been released from jail or prison 24 months ago or less; 3) self-identify as having mental health challenges; 4) living or using services in the City of New Haven and 5) be interested in receiving financial guidance.
- Ineligibility Criteria for the Financial Health and Mental Health after Incarceration intervention: Persons 1) less than 18 years of age; 2) not have been released from jail or prison 24 months ago or less; 3) not self-identify as having mental health challenges; 4) living or using services in the City of New Haven and 5) be interested in receiving financial guidance.
- Service providers/bank and credit union staff participant must be 1) at least 18 years of age and 2). a financial coach or criminal justice service provider from the New Haven area will participate in training activities during the project's first year as part of our partnership with the NH-FEC and local organizations providing services to the target group. The financial coaches and criminal justice service providers are neither participants nor research staff. These are community service providers. They are providing their usual services available to anyone.

### 5.4 Recruitment Procedures

**Focus groups with trained service providers:** Providers will be contacted using contact information shared during the training and asked if they are interested to participate in the focus group. Those who are interested will receive a Zoom link for the focus group. Prior to beginning the focus group, all participants will receive information about the study and the focus group, will have any questions answered, and will give verbal consent to participate.

At least ten staff working for banks or credit unions in the New Haven area will also participate in training activities during the first phase of the project, as part of our partnership with local banks and credit unions through the BankOn Connecticut Coalition (run by our partner organization, CAHS). At the start of years 2, 3 and 4, people who participated in that training will be recruited for a focus group (3 focus groups over 3 years with 5-8 participants each). Similar procedures utilized for the financial coaches and criminal justice providers focus groups will be utilized.

**Individuals with incarceration histories and mental health challenges:**

All participants will be enrolled in New Haven, CT county. The Peer Wellness Coaches and other research staff members have established long-term trusting relationships

with people in the New Haven community, which will enhance our recruitment efforts. Additional recruitment methods include flyers, word of mouth, and local media advertisement resources and social media. Mental Health and carceral services such as the Connecticut Mental Health Center (CMHC), halfway houses, community supervision programs, and the New Haven Reentry Center will also be approached for recruitment advertisement. If interested, the potential participant will contact the research assistant, and the researcher will answer any questions or concerns of the potential participant.

## 5.5 Consent/Assent Procedures/HIPAA Authorization

- Service providers/bank and credit union staff: Six focus groups will be conducted with trained financial coaches and criminal justice providers (3 focus groups with 10 participants each) and bank staff (3 focus groups with 10 participants each). These focus groups will be conducted after the end of training via an audio- video conferencing platform such as Zoom, approved by Yale University IRB. Participants are providers and will not receive compensation for their participation.
- Once a potential participant expresses interest in the proposed research study (by contacting the research team), the research assistant will give a detailed description of the study, describe what research activities are involved for the participant; review confidentiality and privacy, the risks and benefits of their participation, the importance of the knowledge gained, remind them that participation is voluntary and they may decline/opt-out of the study at any time, without consequence. The research assistant will answer any questions or concerns of the potential participant—if/when they decide to participate, the potential participant will be screened for eligibility. Interested participants will answer screening questions which include age; criminal justice involvement history, mental health history, and interest in receiving Financial Health coaching services. Participants will be screened, consented, and complete their baseline assessments within 30-days prior to their first appointment with the Financial Coach. If the potential participant meets eligibility criteria, they will be offered the option to complete the informed consent process 1) remotely using a smartphone 2) remotely using a tablet/personal computer, where a research assistant will be available to help the participant, or 3) in-person with a research assistant at a mutually agreed upon space in the community, or at [name] PRCH research offices located in New Haven. Prospective participants choosing a remote option will receive instructions to access their assigned study link and unique personal identifier required for participation. Members of our research team will be available for those requiring any assistance (including literacy, both reading and technological).

- Online consent: The participant will read an informed consent form on the screen, which will provide a detailed description of the study, a description of the research activities, format, confidentiality and privacy, risks and benefits, voluntary participation, economic considerations, duration, and withdrawal. The form will clearly state that participants can withdraw participation at any time by closing the browser window, and that they may opt-out of any survey questions by selecting an alternative option (e.g., "I do not wish to answer this question"). *This will not affect payment or result in any consequences.* If the participant would like to consent for participation, they will do so by scrolling down on the consent form screen and actively indicating consent (e.g., click a button stating "I consent") if they agree to the terms of participation. The "I consent" button will indicate they understand their involvement in this online research study, and informed consent will be implied.
- In-person consent process: Research assistants will meet prospective participants at either 1) mutually agreed upon space in the community or (2) at [name] PRCH research offices located in New Haven according to participant preference. The consent process will include all steps as described above, following established IRB approved procedures.
- Following informed consent, the participant will be asked to scroll to the next page to complete a demographic face sheet, then navigate through the online baseline measures by endorsing each item with their selected response (duration approximately 60 minutes). The participant will be able to see their progress by viewing a completion bar located on the survey page. Upon completion of the baseline assessment, the participant will be asked to enter their email address for verification of e-gift card to receive their payment for participation in the online study. The participant may also choose to receive their payment in the form of a physical gift card or cash. Participants will receive a \$40 e-gift card (or physical gift card or cash) for their participation.
- For the 6-month assessments, participants will be offered an opportunity to update any demographic data on the face sheet and complete follow-up measures online by endorsing each item with their selected response (duration approximately 60 minutes). Upon completion of the 6-month assessments, the participant will be asked to enter their email address for verification of e-gift card payment for participation in the online study. The participant may also choose to receive their payment in the form of a physical gift card or cash. Participants will receive a \$40 e-gift card (or physical gift card or cash) for their participation.
- For the 12-month assessments, participants will be offered an opportunity to update any demographic data on the face sheet and complete follow-up measures online by endorsing each item with their selected response (duration approximately 60 minutes). Upon completion of the 12-month assessment, the participant will be asked to enter their email address for verification of e-gift card payment for participation in the online study. The participant may also

choose to receive their payment in the form of a physical gift card or cash. Participants will receive a \$40 e-gift card (or physical gift card or cash) for their participation.

- Qualitative interviews will be conducted with 20 consented randomly selected participants (duration approximately 60 minutes). These interviews will be conducted via an audio-video conferencing platform such as Zoom, approved by Yale University IRB or by telephone or in-person with digital-audio recording. The participant may also choose to receive their payment in the form of a physical gift card, or cash. Participants will receive a \$40 e-gift card (or physical gift card or cash) for their participation.
- Participants will be given an opportunity to refuse digital audio-recording in the qualitative interview, but they will not be able to participate in the qualitative interview. They will be informed that all interviews are confidential.

# 6 Study Methods/Procedures

## 6.1 Study Procedures

The data collection for the research will be done via REDCap. Interested participants will provide informed consent electronically.

Following informed consent, the participant will be asked to scroll to the next page to complete a demographic face sheet, then navigate through the online baseline measures by endorsing each item with their selected response (duration approximately 60 minutes). The participant will be able to see their progress by viewing a completion bar located on the survey page. Upon completion of the baseline assessment, the participant will be asked to enter their email address for verification of \$40 e-gift card to receive their payment for participation in the online study.

For the 6-month assessments, participants will be offered an opportunity to update any demographic data on the face sheet and complete follow-up measures online by endorsing each item with their selected response (duration approximately 60 minutes). Upon completion of the 6-month assessments, the participant will be asked to enter their email address for verification of e-gift card payment for participation in the online study. The participant may also choose to receive their payment in the form of a physical gift card or cash. Participants will receive a \$40 e-gift card (or physical gift card or cash) for their participation.

For the 12-month assessments, participants will be offered an opportunity to update any demographic data on the face sheet and complete follow-up measures online by endorsing each item with their selected response (duration approximately 60 minutes). Upon completion of the 12-month assessment, the participant will be asked to enter their email address for verification of e-gift card payment for participation in the online study. The participant may also choose to receive their payment in the form of a physical gift card or cash. Participants will receive a \$40 e-gift card (or physical gift card or cash) for their participation.

Qualitative interviews will be conducted with 20 consented randomly selected participants (duration approximately 60 minutes). These interviews will be conducted via an audio-video conferencing platform such as Zoom, approved by Yale University IRB or by telephone or in-person with digital-audio recording. The participant may also choose to receive their payment in the form of a physical gift card, or cash. Participants will receive a \$40 e-gift card (or physical gift card or cash) for their participation.

Participants will be given an opportunity to refuse digital audio-recording in the qualitative interview, but they will not be able to participate in the qualitative interview. They will be informed that all interviews are confidential.

**Economic Considerations:**

- Participants will receive \$40 cash, e-gift card, or gift card stipend payments for their participation in baseline, 6-month, and 12-month interview. (N=204 X \$40 X3=\$24,480)
- Participants will receive \$40 cash, e-gift card, or gift card stipend payments for their participation in qualitative interviews. (N=20 X \$40 X 2=\$1600)
- Participants of the CAB will receive a \$100 cash, e-gift card, or gift card stipend payment for their participation in CAB meetings (N=6 participants X \$100 X 4 meetings per year X 4 years = \$9600)
- Four community consultants will receive a \$1000 stipend payment for their participation in community meetings (N=4 X \$1000=\$4000)

**Visit Schedule Table**

	Pre-screening (Pre-consent)	Visit 1 Day 1	Visit 2 Day 14 ±7	Visit 3 Day 28 ±7	Visit 4 Day 42 ±7	Visit 5 Day 56 ±7	Visit 6 Day 365 ±30	Unscheduled Visit
EMR Review Eligibility	X							

Informed Consent		X						
Demographics		X						
Clinical history		X					X	
Height & Weight		X	X				X	
Outcome Evaluation								
Pain Assessment (Brief Pain Inventory)		X			X		X	X
Quality of Life Questionnaire		X	X	X	X	X	X	
Randomization		X						
Control & Experimental Interventions – Occupational therapy		X	X	X	X			
Adverse Events Reporting		X	X	X	X	X	X	X

### 6.1.1 Data Collection

Data will be collected using the REDCap platform. Following informed consent, the participant will be asked to scroll to the next page to complete a demographic face sheet, then navigate through the online baseline measures by endorsing each item with their selected response (duration approximately 60 minutes). The measure packet will include a face sheet with demographic information, service utilization, SF-12V2, Quality of Life measure, ASI, ISEL-12, Adult State Hope Scale, Patient Activation Measure (PAM), Wellness in 8 Dimensions Inventory, Peer Support Service Satisfaction Survey, CMS\_AHC HRSN, Patient Health Questionnaire (PHQ9), SCL-90 Anxiety Subscale, Peer Support Provider Contact Log, Community Connections Index, Empowerment Scale, Financial Distress and Financial Wellbeing Scale, Financial Hardship Strain, Financial Skill Scale, The Financial Self-Efficacy Scale, Money Mismanagement Client Rated Assessment. The participant will be able to see their progress by viewing a completion bar located on the survey page. Upon completion of the baseline assessment, the participant will be asked to enter their email address for verification of e-gift card to receive their payment for participation in the online study. The participant may also choose to receive their payment in the form of a physical gift card or cash. Participants will have the option to have these interviews administered by the research staff or on their own.

These interviews will be administered at baseline, 6-months, and 12 months.

Participants (N=20) will also offered participate in qualitative interviews, a recorded informal conversation regarding their experiences. Questions will be developed with the help of the stakeholders CAB and submitted to IRB for approval prior to implementation. The qualitative interviews will be digitally audio/video recorded. These interviews will take place at the end of the 6-month and 12-month assessments.

In addition to the quantitative and qualitative interviews, the researchers will also be collecting notes from the CAB meetings, stakeholder meetings, focus groups, and peer workers notes and contacts.

### 6.2 Method of Assignment/Randomization (if applicable)

Randomization will take place at the individual level. Participants will be randomized to treatment as usual (regular FCS) or treatment as usual with peer support using a 1:1 allocation ratio. The randomization scheme will be generated by the study statistician and given to the data manager for implementation using the Research Electronic Data Captures (REDCap's) randomization module to maintain allocation concealment. The randomization will be stratified by gender and carried out using random permuted block sizes of 2,4, and 6. Participants will be randomly allocated after completion of the baseline assessment.

### **6.3 Adverse Events Definition and Reporting**

[name] (PI) is responsible for oversight of the DSMP and ensuring adherence to procedures for identifying, monitoring, and reporting potential adverse events (AEs) at each site. AEs will be monitored through frequent communication with recruitment sites and weekly team meetings. In accordance with NIH Reported Events policy, [name] will report all such events to the NIH Program Official and other monitoring entities (i.e., IRB, ISM). Non-serious adverse events, unrelated serious adverse events, unanticipated problems, and protocol violations will be reported annually in the NIH progress report and IRB continuation application and discussed at least quarterly with the ISM. [name] will also notify NIH, in writing, about: any suspension or termination of IRB approval (within 3 business days); deaths related to study participation (immediately and no later than 5 business days of learning of the death); unexpected Serious Adverse Events (SAE) related to study participation (within 10 business days of awareness of the SAE); and unanticipated problems involving risks to subjects or others (within 10 business days). Any serious or continuing noncompliance will be reported to the NIH PO by the Yale University IRB within 10 business days of determination.

As stated in the NIH Reported Events policy, all documentation will contain the following elements: “identifying information for the research protocol; the date on which the event occurred and the date at which the PI became aware of the event; a detailed description of the event and impact on the participant(s); a detailed description of the measures taken (including clinical) in response to the event (if any); confirmation that the appropriate monitoring entities and regulatory bodies have been notified as needed; and a description of any changes to the protocol or other corrective actions that have been taken or are proposed in response to the event.”

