**Individuals with Incarceration Histories and Mental Health Challenges:**

This research study will enroll 204 people (**N=204**) who have been released from jail or prison **24 months ago or less** and who have mental health challenges. Participants will be randomized in two arms – (N=102 participants in each arm). They will be enrolled on a continuous basis starting in month 9 of year 1 until month 4 of year 3. We plan to enroll 36 participants in year one, 118 participants in year two, and 50 participants in year 3. All participants will be enrolled in New Haven, CT county. The Peer Wellness Coaches and other research staff members have established long-term trusting relationships with people in the New Haven community, which will enhance our recruitment efforts. Additional recruitment methods include flyers, word of mouth, local media advertisement resources, and social media. Mental Health and carceral services such as the Connecticut Mental Health Center (CMHC), halfway houses, community supervision programs, and the New Haven Re-entry Center will also be approached for the recruitment advertisement. If interested, the potential participant will contact the research assistant, and the researcher will answer any questions or concerns of the potential participant. If/when they decide to participate in the study, the potential participant will be screened for eligibility. The interested individual will answer screening to determine eligibility. If eligible and still interested, the participant will be invited for an interview for consent and baseline interview. Participants will be screened, consented, and complete their baseline assessments, after which they will be referred to a meeting with the New Haven Financial Empowerment Center (NH-FEC) &CAHS) financial coach, within 30-days of their baseline assessment.

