Participants will be randomized to two arms: Arm #1 financial capability support = a) one-on-one financial coaching, which entails monthly or more frequent meetings with a financial coach; initial meetings are in person, and subsequent meetings can be via zoom, phone or in person, depending on the convenience for the client and b) access to safe and affordable financial services, which includes support with managing any existing bank accounts, or supporting a person to open a new overdraft-free account. Coaches can also help people to access other financial products such as free tax preparation (VITA), credit builder loans, online bank accounts, or other products recommended by our Justice Tech partner.

Arm #2 with peer support = in addition to financial capability support will also be offered one-on-one peer support from a trained Recovery Support Specialist...during the period they are receiving the intervention. Wellness coaches will provide weekly meetings (30 to 60 minutes duration).

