## 7.7 Data Monitoring

[name] (MPI) is responsible for monitoring all study activities on a day-to-day basis. [name] will hold weekly research team meetings and discuss protocol and implementation issues, review adverse events, and discuss preliminary or incidental findings. We will also meet quarterly with our Advisory Council and ISM. Data analysis will be ongoing throughout the research period. Trial stopping rules include a greater than expected morbidity or mortality rate, patterns of unanticipated negative findings associated with the intervention, or interference/hindering of the administration of routine medical and behavioral health care that cannot be resolved by an NIH-approved protocol or DSMP change.

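### Adverse events are found passively, and only the peer-support arm adds weekly sessions whose notes reach the researchers, so recorded counts are liable to differ by arm through contact alone

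*Protocol*

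**What the plan says.** Section 6.3 describes how events come to notice: "AEs will be monitored through frequent communication with recruitment sites and weekly team meetings". Section 7.7 adds that the weekly research team meeting reviews adverse events.

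Section 6.1.1 names the instruments in the participant packet one by one, and none is an adverse-event form. On timing and mode it says "These interviews will be administered at baseline, 6-months, and 12 months" and "Participants will have the option to have these interviews administered by the research staff or on their own".

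Regular contact differs by arm (Section 4). Both arms receive "one-on-one financial coaching, which entails monthly or more frequent meetings with a financial coach". For Arm 2 the protocol adds "Wellness coaches will provide weekly meetings (30 to 60 minutes duration", and under Section 6.1.1 the researchers collect the peer workers' notes and contact records. The recruitment text in Section 4 groups the peer coaches with research staff: "The Peer Wellness Coaches and other research staff members have established long-term trusting relationships". Of the coaches whom Arm 1 sees, Section 5.3 says "The financial coaches and criminal justice service providers are neither participants nor research staff".

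The stopping rules in Section 7.7 cover morbidity or mortality above expectation, "patterns of unanticipated negative findings associated with the intervention", and unresolved interference with routine care. No expected rate or threshold is given.

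The visit table in Section 6.1 marks adverse-event reporting at every visit.

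**The concern.** When nobody asks about events on a schedule, the number recorded depends on how often a participant meets someone who will pass an event on. Here that frequency is tied to the randomised factor. Arm 2 has a weekly one-to-one session that feeds the study's records. Arm 1 has no matching channel, and participants recruited by flyer, word of mouth or social media may not be followed by any recruitment site.

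Two consequences are possible for monitoring. Extra observation in Arm 2 could look like a pattern associated with the intervention. Under-counting in Arm 1 could hold the pooled rate down and blunt the rule about rates above expectation. Arm 1 participants are also less likely to have an event noticed and followed up.

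**Working it through.** **1. Figures in the plan.** The protocol gives no adverse-event rate, detection rate or stopping threshold, so there is no figure on this point to reproduce. The only planned number used below is 102 per arm (Section 7.1). It is consistent: a two-sample t-test for 0.5 SD at 90% power and two-sided 5% needs 85.03, rounded up to 86 per arm, and 86 / 0.85 = 101.2, rounded up to 102.

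**2. Planned contacts.** Inputs: coaching at its monthly minimum in both arms, and one peer session a week in Arm 2 (Section 4). The length of the intervention is not stated, so 6 and 12 months are both shown.

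| Assumed length | Arm 1 meetings | Arm 2 meetings | Ratio |
|---|---|---|---|
| 6 months | 6 | 6 + 26 = 32 | 32 / 6 = 5.3 |
| 12 months | 12 | 12 + 52 = 64 | 64 / 12 = 5.3 |

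If the peer coaches are counted as research staff, contacts with research staff after baseline are 1 (6 months) or 2 (12 months) interviews in Arm 1, against 1 + 26 = 27 or 2 + 52 = 54 in Arm 2. Interviews may be self-completed, so the Arm 1 figure is not guaranteed. The peer counts assume full attendance. Section 1.2 reports 43% retention at week 12 and 32% at week 22 in the team's earlier peer-driven programme, so actual contact may be well below plan.

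**3. Illustration of unequal detection.** Let the true risk p be the same in both arms, with detection s1 in Arm 1 and s2 in Arm 2. The recorded risk ratio is (p × s2) / (p × s1) = s2 / s1. The pooled recorded rate is (s1 + s2) / 2 of the true rate. The last three columns give the chance that a comparison of 102 v 102 at nominal two-sided 5% would show a spurious Arm 2 excess: Φ[(Δ − 1.96 × SE0) / SE1], where Δ = p × s2 − p × s1, SE0 uses the pooled proportion and SE1 the separate proportions. The protocol plans no such test; it serves only as a yardstick. All p and s values are assumptions, with s2 = 90%.

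| s1 | Ratio | Pooled / true | p = 10% | p = 20% | p = 30% |
|---|---|---|---|---|---|
| 90% | 1.0 | 90% | 2.5% | 2.5% | 2.5% |
| 80% | 1.12 | 85% | 4% | 6% | 7% |
| 60% | 1.5 | 75% | 13% | 22% | 34% |
| 50% | 1.8 | 70% | 20% | 38% | 56% |
| 30% | 3.0 | 60% | 44% | 76% | 92% |

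Worked row, p = 20%, s1 = 60%: recorded risks are 0.12 and 0.18, SE0 = √(2 × 0.15 × 0.85 / 102) = 0.0500, SE1 = √((0.12 × 0.88 + 0.18 × 0.82) / 102) = 0.0498, and Φ[(0.06 − 0.098) / 0.0498] = Φ(−0.76) = 0.22.

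**4. The visit table.** Its visits fall on Days 1, 14, 28, 42, 56 and 365, with no 6-month visit, and it lists a pain inventory and occupational therapy. None of this matches the baseline, 6- and 12-month schedule. Its adverse-event row therefore cannot be read as a working schedule for this trial, and it conflicts with Section 6.3.

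**The case against.** A fair defence has several parts.

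- **Arm 1 is not cut off.** A reader might infer that its events cannot reach the team before month 6. The protocol does not support that. Sections 2.2 and 6.4 make the research team's contact information available through the coaches, coaching is at least monthly, and Section 4.2 has researchers spending time with participants around coaching sessions, without limiting this to one arm. What is missing is a planned, active route.
- **Both arms answer the same symptom measures**, including the PHQ-9 and an anxiety subscale, and recidivism comes from a public database. This stands. Symptom scores at two follow-ups do not, however, identify individual events.
- **No comparison of harms by arm is planned, and the stopping rule is not written as one.** Section 3.2 treats the coaching itself as the intervention, with or without peer support. A reader might infer that the stopping rule is already biased or will fire falsely. With no threshold and no defined contrast, only susceptibility can be shown.
- **Peer coaches' status as research staff rests on recruitment wording**, while Sections 2.2 and 6.4 list coaches and the research team separately. The asymmetry does not depend on that label, because peer notes go to the researchers either way.
- **The study is stated to be minimal risk, an independent safety monitor reviews events, and Section 8.7 points to a human-subjects section not shown here**, which may hold event forms. These points lower the stakes. The monitor can review only what is captured, and any such form should be named in Section 6.3.
- **Setting peer-session events aside could weaken safety**, since harms of peer support may surface there first. This is correct, and the fix keeps them in monitoring.

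**Conclusion.** The point holds as a liability. Passive detection, a packet without event items and a reporting channel present only in Arm 2 make a higher recorded count in Arm 2, and under-counting in Arm 1, the expected direction if true risks are equal. That rests on peer sessions taking place and on their notes being read for events.

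The size is not estimable from the protocol. The ratios of 1.12 to 3.0 and the pooled rates of 85% down to 60% of truth are illustrations built on assumed detection rates, and should not be quoted as the bias in this trial. The contact ratio of 5.3 follows from the stated meeting frequencies at full attendance.

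The efficacy sample size is unaffected. This is a worthwhile, low-cost improvement to safety capture. It belongs in the protocol because an analysis plan cannot recover events that nobody asked about.

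**What to change.** 1. Add the same short adverse-event questions to the 6- and 12-month REDCap packet for both arms, and name them in Sections 6.1.1 and 6.3.
2. Add a source field to the adverse-event record (interview item, recruitment site, financial coach, peer session, other).
3. Base any by-arm summary of events on the sources common to both arms, and list peer-session events separately by source.
4. Keep every event from every source, including peer sessions, in safety monitoring and in the independent safety monitor's review of the Section 7.7 stopping rules, with the source shown.
5. Reconcile the adverse-event row of the visit table in Section 6.1 with Section 6.3 and with the actual assessment schedule.

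The cost is a few packet items and one data field. The downsides are a slightly longer interview and reliance on six-month recall. The items will also miss people who do not return (Section 7.1 allows 15% missing at 6 months), which is a further reason to keep the other sources in monitoring. The sample size does not change.
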